**Table 2 Schedule of events – Overview Enrolment to End of Study**

Week	Enrolment and treatment period (Week 25 to 104)					ET a
	25	38	52	78	104/ END	
Informed consent	X					
Eligibility criteria	X					
Concomitant therapy	X					X
Physical examination b	X					X
Neurological examination			X		X	X
Height & head circumference			X		X	X
Weight c	X					X
Vital signs d	X					X
12-lead ECG			X		X	X
Antihistamine e	X					
SOBI003 administration f	X					
Adverse events	X					X
Anesthesia/sedation g for:						
CSF sampling (PK, ADA, HS)			X		X	
CSF sampling (future research) h			X		X	
MRI (brain, liver, spleen)			X		X	
Blood sampling for:						
Safety laboratory		X	X	X	X	X
Immunogenicity		X	X	X	X	X
HS		X	X	X	X	X
PK		X	X	X	X	X
Future research h			X		X	
Urine collection for:						
Safety laboratory (Dipstick)		X	X	X	X	X
HS		X	X	X	X	X
Actigraphy (sleep pattern) i			X		X	
BSID-III/KABC-II (neurocognition, language, motor function) j			X		X	X
Parent/caregiver questionnaires:						
VABS-II			X		X	X
CSHQ i			X		X	
PedsQL, incl. Family Impact Module			X		X	X

a In case of Early Termination (ET) of SOBI003 administrations, the assessments should be completed as soon as possible after decision of treatment withdrawal.

b General appearance and skin at the infusion site are examined prior to start of each infusion and within 1 hour of completion of each infusion. On Weeks 52 and 104, as well as at Early Termination, a complete physical

examination (general appearance, skin (including potential reactions around the infusion site), eyes, ears, nose, neck, lymph nodes, throat, heart, lungs, abdomen, musculoskeletal system and extremities) is conducted.

c During the treatment period, body weight is assessed at approximately 4-week intervals to determine the actual SOBI003 dose to be administered. Weight is therefore obtained prior to preparation of the SOBI003 infusions solution at Enrolment (Week 25) and every 4th week during the study. The weight is obtained either the day prior to the infusion or the day of infusion.

d Vital signs includes blood pressure, heart rate, body temperature, respiratory rate and oxygen saturation measured by pulse oximetry. At each infusion, assessments are done pre-infusion, mid-infusion and within 1 hour after end of infusion. If dose is adjusted, vital signs are measured according to 7.5.5.4.

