### **9.2 Definition of study populations**

The following analysis sets will be used in the statistical analyses.

Safety analysis set (SAF): The SAF will consist of all patients who received at least 1 dose of IMP.

The full-analysis set (FAS) is the efficacy analysis set which will consist of all patients enrolled in this extension study, and all patients in the NH study with a rapid progressive disease having a baseline age of 12-72 months (in the DQ analyses).

PK analysis set (PK): The PK set will consist of all patients where at least one SOBI003 dose has been administered correctly and where SOBI003 serum or CSF concentration data is available without any protocol deviation interfering with these results.

Immunogenicity analysis set (IAS): The IAS will consist of those subjects in the safety analysis set who have sufficient blood samples taken for ADA testing at baseline (screening visit) and at least one post-dose time-point

The SAF is used for the safety analysis, the FAS is used for the secondary and explorative efficacy variables.

A subpopulation of the FAS patients who are up to 30 months of age and in the FIH (SOBI003-001) study was initially assigned a dose at least as high as the dose selected for a planned phase III study will be included in future primary analysis population for demonstrating efficacy using combined data from the FIH study and the extension study, the Phase III trial and the corresponding patients in the NH study (control patients), consisting of the 14 patients with a rapid progressive MPS IIIA disease and a baseline age of 12 to 72 months.

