### 9.3 Estimands

There will be a de facto estimand in the study, which is the primary estimand for the evaluation of efficacy. The estimand is the change in

- cognitive decline in all the patients from the population captured by the inclusion and exclusion criteria (see Sections 4.2.1 and Section 4.2.2) and the part of the NH population with a rapid progressive disease having a baseline age of 12-72 months, irrespectively of other medications used and adherence to treatment, and estimated by a repeated measures model of the change from baseline in DQ as described in Section 14.1.
- decline in HS levels in CSF in all the patients from the population captured by the inclusion and exclusion criteria (see Sections 4.2.1 and Section 4.2.2) irrespectively of other medications used and adherence to treatment, and estimated by a repeated measures model of the change from baseline in HS as described in Section 14.1.

To address foreseeable inter-current events, such as drop-outs, all missing values will be imputed (see Section 9.4.4) in accordance with the treatment policy principle. A sensitivity analysis will be performed where no imputations are performed, but all values are used: If a patient has a missing value in any assessment, then the same patient's non-missing scores will be used in the repeated measures model. The repeated measures model (see Section 9.4.4) handles missing values based on the missing at random (MAR) assumption. One further sensitivity analysis for DQ will address this assumption based on zero imputations, the rationale being that the patients not assessed are those expected to have a severe DQ decline. Other sensitivity analyses for this purpose will be tipping point analyses.

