2) The other type of prediction ( $p_2$ ), will be calculated by the use of a population derived slope, estimated based on the repeated measures model in Section 9.4.4 (without imputations), and a patient observation. There will be two cases; If the patient has one or more observations on the same side of  $tp$  as  $v$  (including a possible observation at  $tp$ ), then the nearest observation will be used together with a slope, which is based on the population (treated or untreated) of the same status as the side of  $tp$  where the prediction time point is situated, as well as the interval relative the visits which contain the prediction time point. The other case is when there is no observation on the same side of  $tp$  as  $v$  (and no observation at  $tp$ ). In this case, a prediction at  $tp$  will first be calculated, based on the same method as described above (under 2) but on the other side of  $tp$ , i.e. the nearest observation relative  $tp$  on the other side of  $tp$  will be used together with a slope based on the population (treated or untreated) of the same status as the side of  $tp$  where this nearest observation time point is situated, as well as the interval relative the visits which contain the  $tp$ . This prediction at the  $tp$  is in then used to predict  $v$  as described under the first case (under 2).

For each missing value  $v$ , the following algorithm is used to impute  $v$  by  $i$ :

If  $p_1$  does not exists, then  $p_2$  is used, i.e.,  $i = p_2$ .

Otherwise, a weighted average will be used for the imputation:  $i = w_1 p_1 + w_2 p_2$ , where  $w_1 = \exp(-\lambda \ln(2)/3)$  and  $w_2 = 1 - \exp(-\lambda \ln(2)/3)$  and  $\lambda$  is the distance in months between the time point for prediction and the nearest available non-missing patient assessment time point. The exponential function is motivated by an exponential decrease of relevance of individual patient data relative to population data with increasing time, and the coefficient  $\ln(2)/3$  is chosen such that population data reach the same weight as individual patient data after 75 % of the distance between 2 visits, i.e. 3 months. When individual patient data is available near a missed visit, the patient data weight is near 100 %, and when the distance is near one year on the other hand, the individual patient data weight has decreased to nearly 6 %.

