The second key efficacy endpoint related to the second key secondary objective is the change from baseline in HS levels in CSF at Week 104 after start of SOBI003 treatment in the FIH study (SOBI003-001).

For the purpose of the multiple testing procedure (see Section 14.3), the linear repeated measures analysis with untransformed HS levels in CSF will be used, identical to the DQ analysis with the exception of the treatment factors.

The time effect is used to judge the HS level change in CSF. The null hypothesis of no change will be tested with a significance test for the time-effect in the first step of the multiple testing procedure (see Section 9.4.5). The difference between 104 weeks and baseline will be used as the contrast of interest for the test. Missing HS values will be imputed according to the same methodology as for the missing DQ values.

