9.1 Handling of missing data

All missing DQ values and HS in CSF values will be imputed. The procedure is fully described in Section 14.1. A sensitivity analysis will be performed where no imputations are performed, but all values are used: If a patient has a missing DQ score in any assessment, then the same patient's non-missing scores will be used in the repeated measures model. The repeated measures model (see Section 14.1) handles missing values based on the MAR assumption. One further sensitivity analysis will address this assumption based on zero imputations (see Section 14.1.1), the rationale being that the patients not assessed are those expected to have a severe DQ decline. Another sensitivity analysis for this purpose will be a tipping point analysis, see Section 14.1.1.

If an adverse event (AE) has a completely missing onset date, then the AE will be considered a TEAE, unless the (partial) stop date indicates differently. A medication with a completely missing start date is considered a prior medication. A medication with a completely missing stop date is considered a concomitant medication. If an AE or a medication has a partial missing start or stop date, the following rules will be used to impute the date. The imputed date will be used to determine whether it is a TEAE for adverse event, or a prior or concomitant medication.

Table 1 Partial date derivation

Partial Missing Start or Stop Date	Derived Start Date	Derived Stop Date
Missing month and day, and the year is present	January 1 st of that year or first dose date if the year is the same as the year of first dose date	December 31 st of that year

Partial Missing Start or Stop Date	Derived Start Date	Derived Stop Date
Missing day, but year and month are present	First day of that month or first dose date if the year and month are the same as the year and month of first dose date	Last day of that month
Missing month, but year and day are present	Missing month derived as January or same as first dose month if the year is the same as the year of first dose	Missing month derived as December

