All missing values will be imputed. For a patients who stops treatment, let tp denote the turning point, i.e., the time point when the patient stops treatment. The patient's assessments as well as the time points for prediction are classified as being on either side of the turning point or at the turning point: prior to tp , at tp , or after tp . For patients who does not stop treatment, let $tp = \infty$, i.e., every time point is considered as prior to the tp . Let v denote a missing value to be imputed for a patient. The imputations will be based on two categories of predictions.

1). If the patient has two or more observations on the same side of tp as v (including a possible observation at tp), then v is considered as *exclusively patient-predictable* (p_1), i.e., it can be predicted by simple linear regression based only on the patient's data (intra-or extrapolation). On the other hand, if only one or zero observations exists on the same side of tp (from the particular patient) as v (including a possible observation at tp), then it is considered as *non-predictable exclusively* from the patient's data.

2) The other type of prediction (p_2), will be calculated by the use of a population derived slope, estimated based on the repeated measures model in Section 14.1 (without imputations), and a patient observation. There will be two cases: If the patient has one or more observations on the same side of tp as v (including a possible observation at tp), then the nearest observation will be used together with a slope, which is based on the population (treated or untreated) of the same

status as the side of tp where the prediction time point is situated, as well as the interval relative the visits which contain the prediction time point. The other case is when there is no observation on the same side of tp as v (and no observation at tp). In this case, a prediction at tp will first be calculated, based on the same method as described above (under 2) but on the other side of tp , i.e., the nearest observation relative tp on the other side of tp will be used together with a slope based on the population (treated or untreated) of the same status as the side of tp where this nearest observation time point is situated, as well as the interval relative the visits which contain the tp . This prediction at the tp is in then used to predict v as described under the first case (under 2).

For each missing value v , the following algorithm is used to impute v by i .

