14.2 The HS endpoint

One of the key secondary objectives is to evaluate the effect of SOBI003 on HS levels in CSF.

To evaluate the effect of SOBI003 on HS levels in CSF linear models are used to model the change from baseline in HS levels as dependent variable, for both logged HS levels and untransformed HS levels, and baseline level and age as continuous covariates, and accumulated dose (including the FIH study) as covariate and sex as factor. The analyses are conducted for each assessment time point: baseline, week 52 and 104.

In addition, linear analyses with HS levels, both logged HS levels and untransformed HS levels, in CSF, serum and urine, as dependent variable, and baseline level and age as continuous covariates, and accumulated dose as covariate and sex as factor will be performed across all assessments (including the FIH study), with assessment as a repeated factor.

For the purpose of the multiple testing procedure (see Section 14.3), the linear repeated measures analysis with untransformed HS in CSF levels will be used, identical to the DQ analysis with the exception of the treatment factors.

The time effect is used to judge the HS level change in CSF. The null hypothesis of no change will be tested with a significance test for the time-effect in the first step of the multiple testing procedure (see Section 14.3). The difference between 104 weeks and baseline will be used as the contrast of interest for the test.

The evaluation of the effect of SOBI003 on HS levels in serum and urine will utilize the same models as mentioned above for HS levels in CSF.

The HS levels including change from baseline will also be summarized using descriptive statistics: n, mean, standard deviation (SD), standard error of the mean (SE), median, minimum and maximum. The HS change from baseline will also be presented as percentages. In addition, HS levels, change from baseline in HS levels and change from baseline in HS levels expressed as percentages will be presented in figures: by subject as well as mean graphs.

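### Step 1 (CSF HS) borrows the DQ imputation rule: after treatment stop the rule needs an untreated slope that the HS model lacks, and where it can be run it lifts type I error above 5%

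*Protocol*

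**What the plan says.** - **HS imputation.** Protocol 9.4.4.1: "Missing HS values will be imputed according to the same methodology as for the missing DQ values". SAP 9.1: "All missing DQ values and HS in CSF values will be imputed", with the procedure referred to SAP 14.1, the DQ section. Neither document has an HS-specific rule. Protocol 9.3 and SAP 6 give the reason: "To address foreseeable inter-current events, such as drop-outs, all missing values will be imputed", under a treatment policy principle.
- **The DQ rule.** Each imputed value needs a prediction p2: a patient observation projected along a population slope taken from the repeated measures model fitted without imputations. Protocol 9.4.4.1 describes that slope as one "which is based on the population (treated or untreated) of the same status as the side" of the stopping time on which the missing time point lies. SAP 14.1 repeats this ("a slope, which is based on the population (treated or untreated) of the same" status). After a stop, the slope is the untreated one.
- **The HS analysis.** SAP 14.2 makes the HS model "identical to the DQ analysis with the exception of the treatment factors". Protocol 9.2 and SAP 8.2 admit the controls only for DQ: "all patients in the NH study with a rapid progressive disease having a baseline age of 12-72 months (in the DQ analyses").
- **Data after a stop.** In Protocol Table 2 the row "CSF sampling (PK, ADA, HS") is marked at Weeks 52 and 104 and not at Early Termination. Protocol 7.5.1.8 lists blood and urine for HS at early withdrawal, but no CSF. Protocol 7.3.3.1 continues the later visits only where possible.
- **The step 1 hypothesis.** Protocol 9.4.5 and SAP 14.3 word it as a difference between treatments. The Synopsis, Protocol 9.4.4.1 and SAP 14.2 test a time effect, Week 104 against baseline, in SOBI003 patients.

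**The concern.** DQ can be claimed as confirmatory only if step 1 succeeds, so the step 1 data set should be fully determined in advance. Drop-out is the event the plan itself names as the reason for imputing, and it is the case in which the HS rule lacks an input. The only slope that a one-group HS model yields is the treated one. Using it after a stop assumes that the drug effect continues, and it adds values that carry no sampling error of their own. The second problem also affects gaps on treatment, where the rule can be run as written.

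**Working it through.** **Inputs.** Protocol 9.1 and SAP 7.1: baseline HS 5.2, SD 1.8, correlation 0.1, 80% fall (0.8 × 5.2 = 4.16), 9 treated patients, stated power 99%. Protocol 9.4.5: two-sided 0.05. Assumed: SD 1.8 at each of three visits, pairwise correlation 0.1, a paired t-test in place of the repeated measures model, and k = 1, 2 or 3 missing Week 104 values (no dropout rate is given).

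**1. The plan's figure.** SD of change = 1.8 × √(2 × (1 − 0.1)) = 2.415. Noncentrality = 4.16 / 2.415 × √9 = 5.17; critical t on 8 df = 2.306. Power is 99.4%, which agrees with the stated 99%.

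**2. Tracing the rule.** Take baseline 5.2, Week 52 at 1.04 (80% lower), treatment stopped between Weeks 52 and 104, and no Week 104 CSF.
- No observation lies after the stop, so the patient's own regression prediction p1 does not exist and the imputed value is p2.
- p2 goes from Week 52 to the stop on the treated slope, then from the stop to Week 104 on the untreated slope. The HS model does not estimate that slope. Plausible substitutes run from 1.04 (plateau) to 5.2 (back to baseline).
- If treatment stops before Week 52 and Week 52 CSF is taken, there is one post-stop observation. p1 is again absent and p2 again needs the untreated slope.
- If treatment is not stopped, the rule runs. At 12 months w1 = 2^(−12/3) = 0.0625, so the treated-slope prediction has weight 0.9375.

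**3. Type I error, Week 52 observed.** Simulated under no change, setting Week 104 = Week 52 + mean Week 52–104 change in the patients with data. The on-treatment row adds the weight of 0.0625 on the patient's own line through baseline and Week 52.

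| Handling | k=1 | k=2 | k=3 |
|---|---|---|---|
| Treated slope from Week 52 | 6.1% | 7.5% | 9.4% |
| Full rule, on-treatment gap | 5.9% | 7.2% | 8.8% |
| Observed values only | 5% | 5% | 5% |
| Change set to 0 | 4.8% | 4.6% | 4.1% |

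A pairwise correlation of 0.5 leaves the first two rows essentially the same.

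**4. Type I error, Week 52 also missing.** If baseline is the nearest value, the fill-in is the mean change of the others. The sum of squares does not grow while the divisors do, so t is multiplied by √(n(n−1)/((n−k)(n−k−1))) = 1.134, 1.309, 1.549. Type I error = 2 × P(T on n−k−1 df > 2.306/factor) = 8.1%, 12.9%, 19.7%.

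**5. Power at the 80% fall.** Observed values only (noncentral t, n = 8, 7, 6): 98.5%, 96.4%, 91.6%. Change set to 0: 98.4%, 95.9%, 89.1%. Treated mean change substituted: 99.4% throughout.

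**6. The estimate.** If patients who stop return fully to baseline, the true mean reduction is 80 × (9−k)/9 = 71%, 62%, 53%. A treated substitute still reports about 80%.

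**The case against.** **The rule may be runnable after all.** Since the HS analysis drops the treatment factors, the treated/untreated split could be read as dropping out too, leaving the single HS slope. This is a fair reading, but neither document states it, and it leads to the first row of the table in step 3.

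**The inflation is a separate matter from the missing slope.** This stands. It comes from single imputation with a slope estimated in the same patients, so it also affects on-treatment gaps. Adding a fixed external slope of zero to Week 52 gave 4.9% to 5.1%. The missing slope leaves the value undefined; it does not itself cause the inflation.

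**A reader might quote 8%, 13% or 20%.** The documents do not support those as general figures. They need Week 52 CSF to be missing as well. Every enrolled patient completed the first-in-human study, whose dose selection uses CSF HS (Protocol 7.2), and its data are pooled (SAP 5.2). A later value than baseline may therefore exist, although Protocol 9.4.4.1 lists only baseline, Week 52 and Week 104 for the model.

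**A reader might infer that the value must be picked after the data are seen.** That does not follow. Protocol 9.4.1 has the SAP completed before database lock, so the gap can still be closed in time.

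**Step 1 seldom turns on this, and sensitivity analyses exist.** At the 80% fall this is so. SAP 14.2.1 plans a no-imputation analysis and a tipping-point analysis, but neither decides step 1.

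**Observed values under MAR sit uneasily with a treatment policy estimand.** This also stands: if patients who stop revert, the estimate is as optimistic as with a treated substitute. What improves is the type I error. Setting change to 0 keeps type I error below 5% and costs little more power, so it belongs beside the main analysis.

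**Conclusion.** The point holds in two linked parts. First, the stated rule gives no value for a patient who stops treatment and lacks Week 104 CSF. With complete data, or with gaps only on treatment, it can be run. Second, where it is run, or if the treated slope is used after a stop, step 1 type I error is about 6%, 7.5% or 9.4% with 1, 2 or 3 of 9 Week 104 values missing and Week 52 observed (slightly lower for on-treatment gaps). These figures rest on the paired t-test simplification, equal SDs, the assumed correlation and assumed missing counts.

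The practical effect at the planned 80% fall is small: power is at or above 89% under every handling shown. A smaller effect would make the choice matter more. At an assumed 45% fall with two such patients, the chance of passing step 1 runs from 55.5% (return to baseline) to 78.5% (treated mean change), against 72.1% with complete data. The 45% is borrowed from the modelled brain figure for the lowest dose in Protocol 5.1.3 and is not a CSF estimate.

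The between-treatment wording of step 1 is a separate drafting conflict. Only the within-group test can be run, because HS has no comparator. This is worth correcting because step 1 gates the DQ claim; it does not show that step 1 would fail.

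**What to change.** Before database lock:

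- **(a)** In Protocol 9.3 and 9.4.4.1 and SAP 6, 9.1 and 14.2, let the repeated measures model on observed HS values, already planned in SAP 14.2.1, decide step 1 in place of the DQ-rule imputation. Keep the HS tipping-point analysis. Add return to the patient's own baseline after treatment stop as a prespecified sensitivity analysis, because the plan declares a treatment policy estimand.
- **(b)** In Protocol 9.4.5 and SAP 14.3, state the step 1 null as no change from baseline in CSF HS at Week 104 within SOBI003 patients.

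The cost is wording only, with no new data. With 1, 2 or 3 of 9 values missing, step 1 power falls from 99.4% by 0.9, 3.0 or 7.8 points. The step 1 estimate then relies on MAR and would overstate the reduction if patients who stop revert (step 6 of the working). The own-baseline and tipping-point analyses are there to expose that.
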